6.3 Study Procedures

Medical History and Physical Examination:

During the screening visit, each patient will be questioned concerning medical history. Medical conditions, current medication use, and drug allergies will be recorded. A complete physical examination will be performed by a physician investigator. At Visits 1 and 2, inquiry into adverse events, new symptoms, and medication use will be performed, as will a focused physical examination (vital signs, head, neck, pulmonary and cardiac exams).

Vital Signs:

Temperature, respiration rate, heart rate, oxygen saturation, and blood pressure will be recorded at each study visit prior to pulmonary function tests.

Spirometry:

Spirometry will be performed at screening to determine eligibility. At visits 1 and 2, spirometry will be performed to assess efficacy. On each occasion, the best of 3 trials, based on ATS/ERS criteria. The best FVC, FEV₁ and FEF₂₅₋₇₅ (from trial with highest FVC+FEV₁ sum) will be recorded (absolute value and % of predicted). If subject accidentally uses bronchodilator the morning of visit, spirometry will be collected in the same fashion at the next visit.

Pregnancy Test:

Every female of childbearing potential (first menses has occurred) will have a urine pregnancy test conducted before each study visit. If either of these tests is positive, the patient will be withdrawn from the study.

Measurement of MCC:

MCC measurement will be performed at baseline (Visit 1) and following 14 +/- 2 days of Bronchitol self-administration (Visit 2). Site staff will confirm that the subject meets other eligibility for the procedure (i.e., is not pregnant, symptomatic and has withheld the required medications before proceeding with the MCC procedure. A transmission scan (solid sheet containing Co57, placed in front of the body) of the subject's lungs will be obtained. Detailed instruction will be included in a Study Specific Procedure document. For each measure of MCC, the subject will inhale an aerosol of sulfur colloid labeled with Tc99m. Inhalation will occur until ~40 μ Ci of radioactivity is deposited in the lungs of subjects, which typically takes approximately two minutes. An initial deposition scan will then be recorded within 5 minutes of completing the inhalation, after clearing the oropharynx of activity by drinking a small glass of water. The subject will then remain seated in front of the gamma camera while continuous two-minute images are recorded. The subject will be expected to remain aligned on camera for the first 34 minutes of the scan and then for the first 4 minutes out of each 10-minute epoch until 94 minutes has elapsed. During the first 64 minutes of imaging, subjects will be encouraged to suppress spontaneous coughing so that cilia-driven clearance can be assessed. From 64—94 minutes, they will voluntarily cough through a peak flow meter, to achieve a total of 60 coughs during this interval, to assess cough clearance (CC). Voluntary coughs will be dispersed evenly during this interval. The peak airflow rate of every fifth voluntary cough will be recorded and averaged. Spontaneous cough frequency will be

recorded throughout the imaging period. Subjects will return to the lab for a 15-minute continuous scan of residual lung activity at 6 hours (± 15 minutes) after the initial deposition scan. The images collected will be uploaded in dicom format to University of North Carolina, Chapel Hill through the secure Accelion MCC fileshare site. Detailed description of this procedure is contained in the SILP MCC Standard Operating Procedure Manual (**Appendix 1**).

Bronchitol Tolerance Test:

Following completion of MCC at Visit 1, all subjects will undergo a Bronchitol Tolerance Test (BTT), which will be administered and performed under the supervision of a healthcare provider who is able to manage acute bronchospasm, to identify patients who will tolerate Bronchitol maintenance therapy. Patients will first have their baseline oxygen saturation (SpO₂(Oxygen saturation)) measured and then will be instructed to use a short-acting bronchodilator 5-15 minutes prior to the first test dose of Bronchitol. They will then be instructed to inhale the contents of 1 capsule of Bronchitol (40 mg inhaled mannitol). One minute following this, the new oxygen saturation will be obtained; if below 90% of the baseline SpO₂, the patient will be considered as having failed the BTT. If above 90% of the baseline SpO₂, the patient will be instructed to inhale the contents of 2 capsules, one capsule at a time. After 1 minute, a new SpO₂ and FEV₁ will be obtained. If the SpO₂ is lower than 90% of the baseline or the FEV₁ is less than 80% of the baseline FEV₁ obtained prior to MCC, the patient will be considered as having failed the BTT. If both measures are above the thresholds, the patient will then be instructed to inhale the contents of 3 capsules, one at a time. After 1 minute, a new SpO₂ and FEV₁ will be obtained. If the SpO₂ is lower than 90% of the baseline or the FEV₁ is less than 80% of the baseline FEV₁ obtained prior to MCC, the patient will be considered as having failed the BTT. If both measures are above the thresholds, the patient will then be instructed to inhale the contents of 4 capsules, one at a time. After 1 minute, a new SpO₂ and FEV₁ will be obtained. If the SpO₂ is lower than 90% of the baseline or the FEV₁ is less than 80% of the baseline FEV₁ obtained prior to MCC, the patient will be considered as having failed the BTT. If both measures are above the thresholds, the patient is considered as having passed the BTT and will continue with home use of Bronchitol until Visit 2. If the patient fails the BTT at any time, they will be terminated from the study. Study staff will use the Bronchitol "Healthcare Practitioner Instructions for Use" worksheet to administer the BTT (Appendix 2).

Quality of Life and Respiratory Symptoms:

The CFQ-R is a detailed, rigorously designed and validated instrument designed to measure quality of life in patients with CF who are 14 years and older¹¹. This instrument was developed as the first CF-specific, health-related QOL measure. The respiratory domain has a 0-100 scale, with higher values signifying less severe symptoms. The CRRSD-CRISS is an 8-item, patient-centered outcome measure evaluating symptom severity over the prior 24 hours in 8 domains central to CF¹². Both questionnaires will be administered during Visits 1 and 2 to assess efficacy of the treatment on symptom burden as a secondary outcome.

Treatment Satisfaction:

The TSQM is a 14-question standardize measure for assessment of treatment satisfaction and has been valued for use of inhaled medications in PwCF¹³. It will be administered prior to MCC measurement at Visit 1 and Visit 2. The TSQM items are answered on 5- or 7-point Likert type scale and cover four domains, corresponding to distinct aspects related to the satisfaction of patients with their treatment (Effectiveness; Side effects; Convenience and Global satisfaction). The questionnaire is scored on a 0-100 scale, with higher values indicated greater satisfaction.

6.3.1 Study Schedule

The following procedures at the specified study visit will be performed in the listed order of conduct:

A. Screening Visit

- Informed consent
- Medical history
- Vital signs
- Urine pregnancy test (for females of child-bearing potential)
- Full physical examination

B. Visit 1 (0 or 14+/-3 days after screening)

- Questionnaire administration
- Vital signs (not required if performed same day as screening)
- Abbreviated physical examination (not required if performed same day as screening)
- Urine pregnancy test (for females of child-bearing potential)
- Spirometry
- Mucociliary clearance measurement
- Bronchitol tolerance test

C. Visit 2 (14 +/- 3 days after Visit 1)

- Questionnaire administration
- Vital signs
- Abbreviated physical examination
- Adverse event assessment
- Spirometry
- Mucociliary clearance measurement

6.3.2 Informed Consent

The patient agrees to participate in the study by signing and dating the informed consent form after the nature of the study has been fully explained and all questions have been satisfactorily answered.

6.3.3 Screening

Screening will be conducted by a member of the study staff. After initial chart review indicating preliminary inclusion/exclusion criteria are met, study staff will discuss the study with the patient in the clinic or via telephone, and if they are agreeable, arrange for a screening visit. At the screening visit, inclusion and exclusion criteria will again be reviewed and if met, informed consent will be obtained. Following this, subjects will undergo medical history review, physical examination, medication review, urine pregnancy testing (if applicable) and spirometry measurement.

6.3.4 Recruitment, Enrollment and Retention

Following screening procedures, informed consent and enrollment into the study, a member of the study staff will determine when Visit 1 can be scheduled based on subjects' last reported use of nebulizer hypertonic saline. Visit 1 can be scheduled as early as the same day as screening, but the subject must report no use of nebulized hypertonic saline within 14 days of Visit 1. If the subject has used hypertonic saline on the day of the Screening Visit, Visit 1 must be scheduled at least 14 days from that point and the subject will be required to withhold hypertonic saline during that time. Study staff will send the subject a reminder prior to Visit 1 via telephone or electronic communication.

At the completion of Visit 1, once the subject has been determined to pass the BTT, study staff will schedule Visit 2 in 14 +/- 2 days. Study staff will send the subject a reminder prior to the visit via telephone or electronic communication.

6.3.6 End of Study and Follow-up

Subject participation will be complete at the end of Visit 2 or at the time of withdrawal for subjects who elect to withdraw early or do not pass the BTT. No further attempts will be made to contact subjects beyond this point for study purposes.

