Probably	An event that follows a reasonable temporal sequence after a study procedure; and that is not explained by any other reasonable hypothesis; and that is unlikely to be explained by the known characteristics of the subject's clinical state or by other interventions.

Possibly	An event that follows a reasonable temporal sequence after a study procedure; but that could readily have been produced by a number of other factors.
Unrelated	An event that can be determined with certainty to have no relationship to a study procedure.

Serious Adverse Experiences (SAE)

An SAE is defined as any AE that results in any of the following outcomes:

- death
- a life-threatening adverse experience
- inpatient hospitalization or prolongation of existing hospitalization
- a persistent or significant disability/incapacity
- a congenital anomaly/birth defect

Other important medical events may also be considered an SAE when, based on appropriate medical judgment, they jeopardize the subject or require intervention to prevent one of the outcomes listed.

Serious Adverse Experience Reporting

Study sites will document all SAEs that occur on an SAE Report Form. The collection period for all SAEs will begin after informed consent is obtained and end after procedures for the final study visit (Visit 2) have been completed.

All SAE Report Forms will be reviewed by the site investigator and sent to the coordinating site (UNC) within one business day of the site learning of the event. Sites will send the SAE report by either:

- Email (scanned copy) to: [contact]
- [contact]

The site will notify the coordinating site of additional information or follow-up to an initial SAE Report as soon as relevant information is available. The coordinating site PI may request additional information related to the SAE. Follow-up information is reported on an SAE Report Form.

In accordance with the standard operating procedures and policies of the Institutional Review Board (IRB), the site investigator will report SAEs to the IRB.

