6.3.7 Removal of subjects

Subjects will be withdrawn from the study if they report pregnancy or test positive on pregnancy testing or if they fail the BTT. Subjects may choose to withdraw voluntarily at any time during the study for any reason. If subject has been given Bronchitol to use at home at the time of withdrawal, study staff will ask that the Bronchitol and inhaler be discarded and

that the subject return to use of airway clearance regimen as prescribed by their primary provider. Subjects who prematurely withdraw will be replaced.

Who6.4 Statistical Method

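### For participants who leave early, SAE collection has no end point and no active means; open SAEs and pregnancies are also left without planned follow-up

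*Combined protocol and SAP*

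**What the plan says.** Section 6.2.2.1 sets both ends of the SAE window. "The collection period for all SAEs will begin after informed consent is obtained", and it is to "end after procedures for the final study visit (Visit 2) have been completed". No other end point is given for a participant who never reaches Visit 2. The SAE criteria include "a congenital anomaly/birth defect". On follow-up the section says: "The site will notify the coordinating site of additional information or follow-up to an initial SAE Report as soon as relevant information is available". It adds: "The coordinating site PI may request additional information related to the SAE".

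Section 6.3.6 closes participation: "Subject participation will be complete at the end of Visit 2 or at the time of withdrawal for subjects who elect to withdraw early". BTT failure is treated the same way. The next sentence reads: "No further attempts will be made to contact subjects beyond this point for study purposes".

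Section 6.3.7 adds: "Subjects will be withdrawn from the study if they report pregnancy or test positive on pregnancy testing or if they fail the BTT". For someone who leaves with drug at home, it has staff ask that the drug and inhaler be thrown away and the usual airway clearance resumed. It mentions no adverse event question and no follow-up of a pregnancy. The pregnancy policy in 6.2.2 consists of urine testing at each visit.

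Three other places bear on this. Section 7.12 has a site physician review the outcome of each adverse event. Section 6.4.3.3 reports the proportion of patients with an adverse event, with exact binomial intervals. Section 5.1 takes BTT failures out of the data analysis, and 6.4.5 restricts the final dataset to those who complete both visits.

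**The concern.** Section 3.3.1 names cough, bronchospasm and hemoptysis as risks of the drug. Participants who leave because of one of these are the ones for whom study contact stops. Their SAE window is either undefined or formally open with nobody asking. No visit falls between Visit 1 and Visit 2, so someone who withdraws during home dosing has had no scheduled adverse event assessment since home dosing began.

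What is at stake is the completeness of a small safety dataset. If early leavers are under-ascertained and stay in the denominator, the reported proportion with an event is biased downwards. If the completer rule also governs the safety tables, they drop out of the proportion altogether. Separately, fetal radiation risk is named in 3.3.1 and birth defect is a listed SAE, yet the plan describes no way to learn a pregnancy outcome.

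**Working it through.** **1. The plan's own figures.** Enrolment (5.3.1): 22 / (1 − 0.10) = 24.4, rounded up to 25, as stated. Power (6.4.2): for a two-sided paired t-test with n = 22, difference 5.4, SD 8.5 and alpha 0.05, the noncentral t gives 81.1%, which agrees with the stated 80% or so. Neither figure is in dispute, and nothing below changes them.

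**2. The sections side by side.**

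| Participant | End of SAE collection (6.2.2.1) | End of study contact (6.3.6) | Result |
|---|---|---|---|
| Completer | After Visit 2 procedures | End of Visit 2 | The two coincide |
| BTT failure | Visit 2, which does not take place | At failure, during Visit 1 | No defined end point; later SAEs not sought |
| Withdraws during home dosing | Visit 2, which does not take place | At withdrawal | No defined end point; later SAEs not sought |
| SAE open at exit | Follow-up passed on if it becomes available | At exit | Outcome reaches the study only by indirect routes |
| Pregnancy found at Visit 2 | Closes at Visit 2 | At exit | Birth falls outside both |

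One detail on the last row: 6.3.6 names elective withdrawal and BTT failure but not withdrawal for pregnancy. That the no-contact sentence applies to her is the natural reading, but it is not spelled out.

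**3. How many leave early.** Inputs: 25 enrolled and 10% early termination, BTT failures included (both 5.3.1).

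- Expected number: 25 × 0.10 = 2.5.
- Chance of at least one early termination for any cause, treating participants as independent: 1 − 0.9^25 = 1 − 0.072 = 0.928, about 93%.
- Illustrative split, assuming that the intolerance rate of about 6% in 3.3.1 is the BTT failure rate: 25 × 0.06 = 1.5 BTT failures and 25 × 0.04 = 1.0 other early leaver. The chance of at least one of the latter is 1 − 0.96^25 = 0.64.

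These figures count early leavers, not missed SAEs. The documents give no rate for SAEs after exit.

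**4. Pregnancy.** Section 3.3.1 requires a test at screening and before each scan. A first positive test at Visit 2 comes after the Visit 1 radioaerosol scan and about 14 days of Bronchitol. Section 6.3.7 then withdraws her, and 6.2.2 provides nothing beyond the test. Participation lasts 2 to 4 weeks (synopsis), so SAE collection closes long before any delivery. The gap arises from 6.2.2, 6.2.2.1 and 6.3.7 together with 6.3.6; deleting the no-contact sentence alone would not close it.

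**5. The safety tables.** Section 6.4.3.3 does not say whether the exclusions in 5.1 and 6.4.5 apply to it. If they do, an event learned from an early leaver would still not be tabulated, so better ascertainment alone would not remove the bias.

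**The case against.** The strongest reply is that the text is milder than it looks, and much of that stands.

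- A reader might infer that all contact is forbidden. Section 6.3.6 limits itself to attempts made for study purposes; clinical contact and reports that participants volunteer are not barred.
- A reader might infer that the SAE follow-up in 6.2.2.1 is impossible to carry out. That section sets no duty to contact the participant and no follow-to-resolution rule. Records and treating clinicians can still supply information, and under 7.12 an outcome could be recorded as ongoing. Follow-up is hampered, not ruled out.
- A reader might infer that a congenital anomaly could never come to light. An unsolicited report is possible, and testing before each scan narrows exposure to conceptions undetected at Visit 1 or occurring afterwards. What is missing is a planned route.
- Stopping the drug is not the same as leaving. Section 6.3.7 lists pregnancy, BTT failure and voluntary withdrawal; someone who stops Bronchitol may still attend Visit 2. At a withdrawal conversation staff could also learn of the event that prompted it.
- A fixed share of the SAE window lost cannot be stated. The documents do not say when leavers leave, and the window opens at consent, which may be the day of Visit 1 or about 14 days before it.

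It is also fair to say that the drug is already indicated for adults with CF, that treatment lasts about 14 days, and that extending follow-up goes beyond reconciling the text. None of this supplies an SAE end point for a participant without a Visit 2, or a means of asking about events after exit.

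**Conclusion.** The point holds in a limited form. Sections 6.2.2.1, 6.3.6 and 6.3.7 do not fit together on three matters: the end of SAE collection without a Visit 2, SAEs open at exit, and pregnancy outcome. The first concerns about 2.5 of 25 participants at the protocol's own rate. The 93% is the chance of at least one early termination for any cause, not the chance of a missed SAE. The second and third can arise for completers too, although their collection window itself shows no conflict.

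The conclusion rests on reading the no-contact sentence as it stands and on finding no other SAE end point in the document. The split between BTT failures and other leavers depends on the 6% assumption and is illustrative only. The primary analysis and the sample size are not affected. This is a cheap improvement to safety reporting and worth making.

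**What to change.** Amend 6.3.6 so that study contact after exit is permitted, where the participant agrees, for three purposes:

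- one telephone AE/SAE check at the originally scheduled Visit 2 date, for anyone who received any Bronchitol and left early (under 6.3.4 a BTT failure is never given a Visit 2 appointment, so define the date for them as 14 days after Visit 1);
- follow-up of SAEs open at exit;
- follow-up of any pregnancy detected in the study to its outcome.

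Align the SAE collection period in 6.2.2.1 with these, and cross-refer from 6.3.7. In 6.4.3.3, state that the AE tables include every participant who received any Bronchitol, BTT failures included, regardless of the exclusions in 5.1 and 6.4.5. Without that last sentence the calls would not necessarily reach the tables.

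Cost: protocol and consent wording, and calls to about two or three participants. Some will decline or be unreachable, and a pregnancy record may stay open after database lock.

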6.3.7 Removal of subjects

Subjects will be withdrawn from the study if they report pregnancy or test positive on pregnancy testing or if they fail the BTT. Subjects may choose to withdraw voluntarily at any time during the study for any reason. If subject has been given Bronchitol to use at home at the time of withdrawal, study staff will ask that the Bronchitol and inhaler be discarded and

that the subject return to use of airway clearance regimen as prescribed by their primary provider. Subjects who prematurely withdraw will be replaced.

Who6.4 Statistical Method

6.4.1 Statistical Design

To determine the effect of visit, and thus Bronchitol administration on clearance, the MCC₆₀ will be analyzed with a paired t-test. As a second step, we will include the effect of skew in a repeated measure model. Inclusion of deposition skew as a covariate in the primary assessment of MCC is an important consideration because increased deposition skew/heterogeneity is associated with faster observed MCC rates. This change in MCC rate reflects increased radio-aerosol deposition in large airways, which have intrinsically faster MCC rates. The described mixed effect model will, therefore, allow us to determine whether there is an effect of treatment (reflected by the visit covariate) on MCC independent of any potential changes in deposition skew. Exploration of other parameters including site location, age, sex, etc. will be performed by visualizing box plots and scatter plots of MCC₆₀ organized by each variable. Remaining secondary outcomes will be evaluated using paired t-tests to determine differences before and after treatment with Bronchitol.

6.4.2 Sample Size Considerations

The proposed sample size of 22 patients enrolled and completing two visits should provide approximately 80% power at a two-sided significance level of 0.05 to detect a treatment effect of 5.4% (absolute change in MCC₆₀). This calculation is based upon prior data, which revealed a standard deviation of within-patient difference of 8.5%. A treatment difference of this magnitude is considered to be both clinically meaningful and achievable, as it approximates the sustained effect observed with HS treatment in patients with CF.

